5.4 Other Restrictions and Precautions

Palliative (limited-field) radiation therapy is permitted, but only for pain control to sites present at baseline and with approval by the IND Sponsor.

Medical marijuana for pain or symptom control will be permitted.

5.5 Definition of an Overdose for this Protocol

Overdose of retifanlimab is defined as:

An overdose is defined as the accidental or intentional administration of any dose of a product that is considered both excessive and medically important. All occurrences of overdose must be reported as SAEs (see **Section 7.5.1** for reporting details). Appropriate supportive treatment should be provided if clinically indicated.

All reports of overdose with and without an AE must be reported within 24 hours to the IND Sponsor and Incyte. Incyte contact information can be found in **Section 7.5.1**.

5.6 Unacceptable Toxicity

Toxicities are defined in the Investigator's Brochure and **Table 4**. Unacceptable toxicities for this protocol that will trigger additional review described below are defined as:

- 1. Any treatment-related > grade 3 AEs. Exceptions include:
 - Asymptomatic laboratory abnormalities (AST, ALT, and bilirubin abnormalities requiring discontinuation as per **Table 4** will be considered unacceptable toxicity)
 - Grade 3 fatigue
 - Grade 3 dermatologic AEs that are considered mild in severity but only considered grade 3 because of >30% body surface involvement including pruritus
 - Diarrhea, nausea, or vomiting that resolves to < grade 3 within 48 hours of maximal intervention
 - Grade 3-4 hyperglycemia or grade 3 endocrinopathies where symptoms are controlled on hormone replacement therapy
- 2. Treatment related blood bilirubin > 5 x ULN or concurrent blood bilirubin > 2 x ULN and AST or ALT > 3 x ULN
- 3. Treatment related eye pain ≥ grade 2 or reduction of visual acuity that does not respond to topical therapy and does not improve to ≤ grade 1 severity within 2 weeks of starting therapy, or requires systemic therapy is an unacceptable toxicity.

Unexpected Grade 3 or greater laboratory abnormalities should be repeated within 24-72 hours if clinically indicated and monitored as necessary to determine if event meets toxicity criteria.

The proportion of treated subjects with unacceptable toxicity will be monitored using a Bayesian stopping guideline. A Beta (1.5, 5.5) prior, representing a toxicity rate of 21%, a slightly conservative estimate, was used in the development of our guidelines. We will halt the accrual and re-evaluate the safety if the posterior probability that the toxicity rate exceeds the 33% boundary is greater than 60%. Toxicity will be monitored continuously. **Table 2** summarizes the stopping boundaries for unacceptable toxicities.

Table 2. The number of unacceptable toxicities needed to trigger stopping guidelines throughout the course of the study.

Number of Subjects	Number of unacceptable toxicities needed to trigger re-evaluation
2	2
3-5	3
6-7	4
5-10	5
11-13	6
14-16	7
17-19	8
20-22	9
23-25	10

Table 3. Probability of triggering a re-evaluation based upon the proportion with an unacceptable toxicity for a range of true toxicity probabilities.

True probability of	Probability of triggering
unacceptable toxicity	stopping guidelines
5%	0.4%
10%	1.8%
15%	6%
20%	14%
25%	27.5%
30%	44.9%
35%	62.3%
40%	78%
45%	89.2%

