13.4 Safety monitoring and stopping guidelines

Adverse events will be monitored during the trial. The occurrence of unacceptable AEs, as defined in **Section 5.6**, at any time during the treatment will be the endpoint for safety monitoring. If the events of unacceptable AEs appear to be higher than 33%, we will temporarily halt the study pending safety evaluation. A Beta (1.5, 5.5) prior, representing a toxicity rate of 21%, a slightly conservative estimate, was used in the development of the stopping guidelines. The therapy will be re-evaluated if the posterior probability that the toxicity rate exceeds the 33% boundary is greater than 60%. **Table 5** summarizes the stopping boundaries for unacceptable toxicities.

Table 5. The number of unacceptable toxicities needed to trigger stopping guidelines throughout the course of the study.

Number of Subjects	Number of unacceptable toxicities needed to trigger re-evaluation
2	2
3-5	3
6-7	4
5-10	5
11-13	6
14-16	7
17-19	8
20-22	9
23-25	10

Operating characteristics of the stopping rule based on 10000 simulations are shown below.

True probability of	Probability of triggering
unacceptable toxicity	stopping guidelines
5%	0.4%
10%	1.8%
15%	6%
20%	14%
25%	27.5%
30%	44.9%
35%	62.3%
40%	78%
45%	89.2%

REFERENCES

- 1. Rahib, L. *et al.* Projecting cancer incidence and deaths to 2030: the unexpected burden of thyroid, liver, and pancreas cancers in the United States. *Cancer Res.* **74**, 2913–2921 (2014).
- 2. Siegel, R. L., Miller, K. D. & Jemal, A. Cancer statistics, 2016. *CA Cancer J Clin* **66**, 7–30 (2016).
- 3. Burris, H. A. *et al.* Improvements in survival and clinical benefit with gemcitabine as first-line therapy for patients with advanced pancreas cancer: a randomized trial. *J. Clin. Oncol.* **15**, 2403–2413 (1997).
- 4. Conroy, T. *et al.* FOLFIRINOX versus Gemcitabine for Metastatic Pancreatic Cancer. *New England Journal of Medicine* **364**, 1817–1825 (2011).
- 5. Von Hoff, D. D. *et al.* Increased Survival in Pancreatic Cancer with nab-Paclitaxel plus Gemcitabine. *New England Journal of Medicine* **369**, 1691–1703 (2013).
- 6. Borazanci, E. *et al.* Adenosquamous carcinoma of the pancreas: Molecular characterization of 23 patients along with a literature review. *World J Gastrointest Oncol* 7, 132–140 (2015).
- 7. Brahmer, J. R. *et al.* Safety and activity of anti-PD-L1 antibody in patients with advanced cancer. *N. Engl. J. Med.* **366**, 2455–2465 (2012).

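### Sections 5.6 and 13.4 attach different halts to the same toxicity trigger (accrual versus the study), so it is unclear whether patients already on retifanlimab continue treatment during the review.

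*Combined protocol and SAP*

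**What the plan says.** Section 5.6 defines the unacceptable toxicities and sets a Bayesian guideline for them. It gives the prior ("A Beta (1.5, 5.5) prior, representing a toxicity rate of 21%, a slightly conservative estimate, was used in the development of our guidelines"), states that "Toxicity will be monitored continuously", and gives the action once the posterior probability of a toxicity rate above 33% passes 60%: "We will halt the accrual and re-evaluate the safety". Table 2 lists the boundaries.

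Section 13.4 takes its events from Section 5.6 and repeats the prior ("A Beta (1.5, 5.5) prior, representing a toxicity rate of 21%, a slightly conservative estimate, was used in the development of the stopping guidelines"), the 33% limit, the 60% threshold and, as Table 5, the boundaries. Its action is worded differently: "If the events of unacceptable AEs appear to be higher than 33%, we will temporarily halt the study pending safety evaluation". A later sentence ties the 60% threshold to a re-evaluation of the therapy and does not say what is suspended meanwhile.

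Section 13.4 counts events occurring at any time during treatment. Section 5.1 gives a 28-day cycle.

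**The concern.** A stopping guideline has two parts: when it fires and what then happens. The first part is identical in the two sections; the second is not. Halting accrual, in ordinary trial usage, stops new patients entering. Halting the study ordinarily reaches further and can include treatment of those already enrolled.

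The difference matters because the rule can fire while other patients are between infusions. Someone must then decide whether those patients receive their next dose before the review is complete. The protocol gives two descriptions of the pause and does not answer that question in either. A safety rule should state what it suspends before it is needed, so that the decision is not made under pressure and can be defended afterwards.

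**Working it through.** **Step 1. Is it one rule or two?** Inputs, all printed in both Section 5.6 and Section 13.4: prior Beta(1.5, 5.5), limit 0.33, posterior threshold 0.60. The prior mean is 1.5 / (1.5 + 5.5) = 0.214, which matches the stated 21%.

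The boundary at n subjects is the smallest x for which P(p > 0.33) > 0.60 when p follows Beta(1.5 + x, 5.5 + n − x). Exact results:

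| x of n | Posterior P(p > 0.33) | Triggers? |
|---|---|---|
| 2 of 2 | 0.621 | yes |
| 3 of 5 | 0.607 | yes |
| 4 of 8 | 0.597 | no |
| 5 of 8 | 0.787 | yes |
| 5 of 10 | 0.658 | yes |
| 9 of 20 | 0.728 | yes |
| 9 of 25 | 0.474 | no |
| 10 of 25 | 0.623 | yes |

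The printed limits reproduce at every n from 2 to 25, provided the row printed as 5-10 is read as 8-10. As printed, that row overlaps the rows 3-5 and 6-7, in both tables. So this is a single trigger, printed twice.

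**Step 2. Set the actions side by side.**

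| | Section 5.6 | Section 13.4 |
|---|---|---|
| What is halted | accrual | the study, temporarily |
| What follows | safety re-evaluated | safety evaluation; therapy re-evaluated |
| Dosing of current patients | not mentioned | not mentioned |
| Who decides on resumption | not stated | not stated |

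The first row is a direct conflict. The third is silent in both sections, so any conflict on dosing arises only by implication from the first.

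**Step 3. Does another section settle it?**

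- Section 5.9 takes off treatment the individual subject who has an unacceptable toxicity. It does not cover the others during a review.
- Footnote 1 of the study calendar (Section 10) allows a cycle to slip by up to a week, with IND Sponsor approval beyond that. It does not address a trial-level halt.
- Section 12.2 describes safety meetings and teleconferences without referring to this rule.
- Section 12.3 gives the Safety Monitoring Committee general oversight, but no stated role in this halt or in lifting it.

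None resolves the scope.

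**Step 4. How often would the question arise?** Exact recursion with a look after each subject from the second onward, each subject fully observed, using the Step 1 boundaries:

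| True toxicity rate | Up to 25 subjects | Up to 7 subjects |
|---|---|---|
| 21.4% (prior mean) | 14.4% | 10.1% |
| 33% | 48.9% | 27.0% |
| 40% | 72.7% | 40.2% |

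The 7-subject column applies if the trial ends after Simon stage 1, which Section 13.1 gives as a 70% chance when the true DCR is 5%.

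The protocol's own operating characteristics, stated in Section 13.4 to come from 10,000 simulations, are higher than the 25-subject recursion: 14% against 11.7% at a 20% rate, 44.9% against 38.3% at 30%, and 78% against 72.7% at 40%. I could not reproduce the printed column from the stated rule. That is a separate matter and does not affect this point.

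**Step 5. Who would be affected?** A trigger at 5 of 10 leaves at most 10 − 5 = 5 subjects without an unacceptable toxicity; a trigger at 9 of 20 leaves at most 20 − 9 = 11. These are ceilings, since some of those patients will already have progressed or left treatment.

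**The case against.** The strongest reply is that the two sections agree in substance. Both describe a pause followed by a safety re-evaluation, and both boundary tables are captioned as triggers for re-evaluation. On this view, halting the study is loose wording for halting accrual. That is possible, but the text does not say it, and the two phrases differ on the one thing a halt must define.

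Several stronger readings are tempting, and the reply succeeds against them.

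- A reader might infer that the protocol contradicts itself outright on dosing. It does not: neither section mentions dosing. The stated contradiction is about what is halted; the uncertainty about treatment follows from it.
- A reader might infer that each site could choose a section and remain compliant, making the month-4 DCR site-dependent. The documents point the other way. Both sections say that we, the trial leadership, will act, and the trigger is described for the trial as a whole. Section 7.5.1 sends unacceptable toxicities to the IND Sponsor within 24 hours, and Section 12.1 makes the Protocol Chair responsible for conduct at all institutions. One central instruction is the natural outcome. The protocol does not say what it would be, but divergence between sites is speculation.
- A reader might ask for new rules on scan timing, or on how a halt counts toward removal for more than two dose delays. Calendar footnote 13 already keeps scans on calendar weeks despite dosing delays, and the Section 5.9 rule is confined to repeated delays for one and the same drug-related toxicity.
- A reader might take the trigger probabilities as a measure of damage. They measure only how often the rule fires.

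What survives the objection is the conflict in scope and the absence of any text that resolves it.

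**Conclusion.** The point holds as a conflict in the wording of a safety stopping rule: one trigger, two stated scopes. Whether enrolled patients continue treatment during the review is unclear by implication, not by explicit contradiction. No boundary or efficacy figure changes, and no effect on the DCR is shown.

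Its practical weight rests on how readily the rule could fire. That is about 14% at the prior mean rate and 73% at a 40% rate if all 25 subjects are fully observed, or about 10% and 40% if enrolment ends at 7. These values assume the row 5-10 means 8-10 and a look after every subject; the protocol's printed probabilities are higher where the same rate is tabulated. The point merits correction because it concerns patient safety and is cheap to settle, not because harm has been demonstrated. Which scope is right is a clinical decision, and this review takes no position on it.

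**What to change.** Reconcile Sections 5.6 and 13.4 so that both carry the same statement of:

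1. what the trigger suspends: enrolment only, or enrolment and treatment of patients already on study;
2. who decides on resumption.

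The clinical team and the Safety Monitoring Committee named in Section 12.3 should choose the scope. The simplest drafting is to state the action once and have the other section refer to it.

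The row 5-10 in Tables 2 and 5 can be corrected in the same edit. If trigger probabilities are quoted in support of the rule, state the number of subjects and the boundaries they assume.

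The cost is one aligned sentence in two places, with no new data, procedures or analyses.

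### Tables 2 and 5 give two toxicity limits at 5, 6 and 7 subjects (row 5-10 should read 8-10), and the printed trigger probabilities fit neither set of limits

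*Combined protocol and SAP*

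**What the plan says.** Section 5.6 defines unacceptable toxicity and monitors its rate continuously. The prior is given as follows: "A Beta (1.5, 5.5) prior, representing a toxicity rate of 21%, a slightly conservative estimate, was used in the development of our guidelines". Accrual is halted for a safety review "if the posterior probability that the toxicity rate exceeds the 33% boundary is greater than 60" per cent. The limits that follow from this appear under "Table 2. The number of unacceptable toxicities needed to trigger stopping guidelines throughout the course of the study", and section 13.4 prints the same rows under "Table 5. The number of unacceptable toxicities needed to trigger stopping guidelines throughout the course of the study". In both tables the rows run 2 (limit 2), 3-5 (3), 6-7 (4), 5-10 (5), 11-13 (6), and so on to 23-25 (10).

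The behaviour of the rule is given in section 5.6 under "Table 3. Probability of triggering a re-evaluation based upon the proportion with an unacceptable toxicity". The same column of figures follows in section 13.4, introduced by "Operating characteristics of the stopping rule based on 10000 simulations are shown below".

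**The concern.** A rule checked after every subject needs exactly one limit at each number of subjects. Here the row 5-10 overlaps the two rows above it. At 5 subjects the tables give limits of 3 and 5, at 6 and 7 subjects they give 4 and 5, and no row begins at 8. A reader who uses the row 5-10 would continue accrual after 3 toxicities in 5 subjects, or 4 in 6 or 7, although the stated rule calls for a halt. The ambiguity falls among the first subjects treated; the first stage of the Simon design is itself 7 patients.

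The probability table ought to show which limits were meant, but it does not: the printed figures are too high for either reading. Those judging whether the safety rule is sensitive enough have been given figures that the rule does not deliver.

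**Working it through.** **Inputs.** Prior Beta(1.5, 5.5), boundary 33%, posterior threshold 60% and continuous monitoring (sections 5.6 and 13.4); first printed limit at 2 subjects; maximum of 25 subjects (last table row and section 1.4); 10000 simulations (section 13.4). The prior mean is 1.5/7 = 0.214, which agrees with the plan's 21%.

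**Step 1: limits from the stated rule.** After x toxicities in n subjects the posterior is Beta(1.5 + x, 5.5 + n − x). The limit at n is the smallest x for which P(rate > 0.33) exceeds 0.60.

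| x / n | Posterior | P(rate > 0.33) | Halt? |
|---|---|---|---|
| 3/5 | Beta(4.5, 7.5) | 0.607 | yes |
| 3/6 | Beta(4.5, 8.5) | 0.524 | no |
| 4/6 | Beta(5.5, 7.5) | 0.744 | yes |
| 4/7 | Beta(5.5, 8.5) | 0.672 | yes |
| 4/8 | Beta(5.5, 9.5) | 0.597 | no |
| 5/8 | Beta(6.5, 8.5) | 0.787 | yes |

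The limit is therefore 3 at 5 subjects and 4 at 6 and 7, and 5 first applies at 8. Over the whole range the rule gives 2: 2, 3-5: 3, 6-7: 4, **8-10: 5**, 11-13: 6, 14-16: 7, 17-19: 8, 20-22: 9, 23-25: 10. Every printed row except 5-10 is reproduced.

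**Step 2: trigger probabilities.** For a true rate p, the number of toxicities is followed subject by subject. At each n from 2 to 25, the probability of paths that reach the limit is added to the trigger probability and those paths are removed. This is exact, with no simulation error. The misprinted reading uses a limit of 5 at 5, 6 and 7 subjects and is otherwise the same.

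| True rate | Printed | Corrected row (8-10) | Misprinted row (5-10) | Printed − corrected (points) |
|---|---|---|---|---|
| 5% | 0.4% | 0.3% | 0.3% | 0.1 |
| 10% | 1.8% | 1.8% | 1.3% | 0.0 |
| 15% | 6% | 5.1% | 4.0% | 0.9 |
| 20% | 14% | 11.7% | 9.8% | 2.3 |
| 25% | 27.5% | 22.8% | 20.3% | 4.7 |
| 30% | 44.9% | 38.3% | 35.7% | 6.6 |
| 35% | 62.3% | 56.1% | 53.8% | 6.2 |
| 40% | 78% | 72.7% | 71.1% | 5.3 |
| 45% | 89.2% | 85.5% | 84.6% | 3.7 |

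At a true rate of 30% the Monte Carlo standard error with 10000 runs is √(0.383 × 0.617 / 10000) = 0.0049, or 0.49 points. The 6.6-point gap is about 13 standard errors (6.6/0.49). The misprinted row is further away, by 44.9 − 35.7 = 9.2 points. A separate simulation of 400000 runs gave 38.2% and 35.6% at 30%, in agreement with the exact values.

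**Step 3: could another assumption explain the printed column?** Keeping the stated prior, boundary and threshold, the largest gap from print is 11.0 points if monitoring ends at 21 subjects and 6.6 points at 25. A later first look, looks every 2 to 5 subjects, limits shifted by one, or a boundary of 1/3 all fit worse than 6.6 points. A looser rule (boundary 0.32, threshold 0.57), whose limits include 4 at 6-8, 5 at 9-11 and 6 at 12-14, comes within 0.5 points at every true rate. That suggests the column came from another version of the rule, but the documents describe none.

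**Step 4: effect of using the wrong row.** Chance of a halt, corrected against misprinted row:

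| By n subjects | True rate 30% | True rate 40% |
|---|---|---|
| 7 | 21.9% vs 13.4% | 40.2% vs 25.5% |
| 10 | 25.9% vs 21.6% | 48.5% vs 43.5% |
| 25 | 38.3% vs 35.7% | 72.7% vs 71.1% |

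**The case against.** The strongest reply is that this is a one-digit slip with little practical reach. The governing rule is written out in full in both sections, and the table only summarizes it. The two rows above the faulty one carry the correct limits, and the order of the rows makes 8-10 the obvious reading. To go wrong, staff would have to pass over two correct rows and use the one out of sequence. Other protection exists: unacceptable toxicities reach the IND sponsor within 24 hours (section 7.5.1), safety meetings are weekly or as needed (section 12.2), and a safety monitoring committee has oversight (section 12.3). The halt is temporary, and the cumulative loss is at most about 2.6 points by 25 subjects. The probability table is descriptive; no decision depends on it, and its 5% and 10% entries agree with the corrected limits.

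Much of this stands. The formula does resolve the overlap, the figures for the misprinted row describe the worst reading, and the harm is mainly a delay early in the trial. It does not rescue the text. A halting limit that staff look up should not require them to recompute a Beta posterior. The faulty entry appears in both tables, so an accident of PDF reading is unlikely. Nor does agreement at low true rates rescue the probability column: it fails at 20% to 45%, where a safety rule has to be judged.

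**Conclusion.** The point holds. Under the plan's own rule, row 5-10 in Tables 2 and 5 is wrong and should read 8-10. The consequence of following it is a lower chance of an early halt: 14.7 points lower by 7 subjects at a true rate of 40% (40.2 − 25.5), shrinking to 1.6 points by 25 subjects (72.7 − 71.1).

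The printed trigger probabilities, taken as a column, match neither set of limits. At true rates of 20% to 45% they exceed the exact values for the corrected limits by 2.3 to 6.6 points. The cause cannot be determined from the documents.

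These results assume that subjects are independent with a common toxicity rate, that each subject's outcome is known before the next check, and that monitoring runs from 2 to 25 subjects.

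One query carries no weight in this conclusion. Item 1 of section 5.6 reads "Any treatment-related > grade 3 AEs. Exceptions include" in the text available here. Taken literally, that would leave the listed exceptions for grade 3 fatigue, grade 3 dermatologic events and grade 3 endocrinopathies with nothing to except. It also sits awkwardly beside "Unexpected Grade 3 or greater laboratory abnormalities should be repeated within 24-72 hours if clinically indicated" in the same section. The sign may be a ≥ lost when the PDF was read.

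**What to change.** 1. In Table 2 (section 5.6) and Table 5 (section 13.4), change the row label 5-10 to 8-10.
2. Re-run the trigger probabilities in Table 3 and in the matching table of section 13.4 with the corrected limits, or state the different assumption behind the printed figures. With checks after every subject to 25, the replacement values are 0.3, 1.8, 5.1, 11.7, 22.8, 38.3, 56.1, 72.7 and 85.5% for true rates of 5% to 45%.
3. Check item 1 of section 5.6 in the source PDF and, only if it prints >, change it to ≥ grade 3. Section 13.4 takes its event from section 5.6 and needs no edit of its own; the safety endpoint for grade 3 or above in section 11.2 is a separate measure.

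The cost is one label in two tables, one repeated calculation and one check of a sign. Design, sample size and patient procedures do not change.

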5.7 WOCBP, Contraception, Use in Pregnancy, Use in Nursing

A WOCBP is defined as any female who has experienced menarche and who has not undergone surgical sterilization (hysterectomy or bilateral oophorectomy) and is not postmenopausal. Menopause is defined clinically as 12 months of amenorrhea in a woman over age 45 years in the absence of other biological or physiological causes. In addition, women under the age of 62 years must have a documented serum follicle stimulating hormone (FSH) level > 40mIU/mL to confirm menopause.

Women treated with hormone replacement therapy (HRT) are likely to have artificially suppressed FSH levels and may require a washout period in order to obtain a physiologic FSH level. The duration of the washout period is a function of the type of HRT used. The duration of the washout period below are suggested guidelines and the investigators should use their judgment in checking serum FSH levels. If the serum FSH level is >40 mIU/ml at any time during the washout period, the woman can be considered postmenopausal:

- 1 week minimum for vaginal hormonal products (rings, creams, gels)
- 4 week minimum for transdermal products
- 8 week minimum for oral products

